##### 9.4.4.2. Ophthalmic Examinations

Ophthalmic assessments will be performed or supervised by a board-certified ophthalmologist or optometrist as specified in the Schedule of Activities (see Section 2) and/or as clinically indicated.

Eye testing will include distance and near visual acuity (best-corrected or pinhole using the Snellen chart and Near Reading Card), Humphrey visual field testing (using the 10-2 protocol with a red-on-white target), and ophthalmoscopy.

Only subjects who pass all other inclusion/exclusion criteria at screening should be sent for these eye examinations. Results from subsequent eye tests during the study will be compared with the screening results to track any changes in subjects' vision.

### 9.4.5. Safety Monitoring

The Lilly clinical pharmacologist will monitor safety data throughout the course of the study.

Lilly will review SAEs within time frames mandated by company procedures. The Lilly clinical pharmacologist will consult with the functionally independent Global Patient Safety therapeutic area physician or clinical research scientist when appropriate, and periodically review

- trends in safety data
- laboratory analytes
- AEs
- product complaints

#### 9.4.5.1. Hepatic Safety Monitoring

If a study subject experiences elevated ALT  $\geq 3X$  ULN, alkaline phosphatase  $\geq 2X$  ULN, or elevated total bilirubin  $\geq 2X$  ULN, clinical and laboratory monitoring should be initiated by the investigator. Details for hepatic monitoring depend upon the severity and persistence of observed laboratory test abnormalities. To ensure subject safety and compliance with regulatory guidance, the investigator is to consult with the Lilly designated CRP/clinical pharmacologist regarding collection of specific recommended clinical information and follow-up laboratory tests.

In the event that safety monitoring uncovers an issue that needs to be addressed by unblinding at the group level, additional analyses of the safety data will be performed by the personnel included in the Unblinding/Blinding Plan.

## 9.5. Pharmacokinetics

In Parts A and B, at the visits and times specified in the Schedule of Activities (Section 2), venous blood samples will be collected to determine the plasma concentrations of LY3323795. A maximum of 5 samples may be collected at additional time points during the study if warranted and agreed upon between both the investigator and sponsor. For subjects participating in the itraconazole interaction (Part C), on the day of LY3323795 and itraconazole coadministration (Day 16), venous blood samples will be collected for measurement of itraconazole and its metabolites at the times specified in the Schedule of Activities for Part C. LY3323795 PK samples will also be drawn on Day 1 and on the day of coadministration (Day 16). Instructions for the collection and handling of blood samples will be provided by the sponsor. The actual date and time (24-hour clock time) of each sampling will be recorded.

For Part B, CSF samples will be collected at the times specified in the applicable Schedule of Activities (Section 2) to determine the CSF LY3323795 and PD biomarker concentrations.

Drug concentration information that may unblind the study will not be reported to investigative sites or blinded personnel until the study has been unblinded.

In Part A, urine samples will be collected for the characterization of renal clearance. Total urine output for 48 hours post investigational product administration will be collected, pooled, and

refrigerated. The final urine sample will be collected at a time that coincides with a PK sample. At the end of the collection period, the total urine volume will be recorded. Urine samples will be used to determine creatinine, quantification of LY3323795, and possible exploratory metabolite identification.

At the visits and times specified in the Schedule of Activities, venous blood samples will be collected to determine serum creatinine measurements.

See [Appendix 5](#) for blood and CSF sampling details.

### 9.5.1. Bioanalysis

Samples will be analyzed at a laboratory approved by the sponsor and stored at a facility designated by the sponsor.

Concentrations of LY3323795 in plasma and in CSF will be assayed using validated liquid chromatography with tandem mass spectrometry (LC/MS/MS) methods. Plasma concentrations of itraconazole will be assayed using LC/MS/MS methods. If appropriate, plasma concentrations of itraconazole metabolites may also be quantified. Analyses of samples collected from subjects who are given placebo are not planned.

Bioanalytical samples collected to measure investigational product concentrations will be retained for a maximum of 2 years following last subject visit for the study. During this time, samples remaining after the bioanalyses may be used for exploratory analyses (eg, metabolism, protein binding).

## 9.6. Pharmacodynamics

At the visits and times specified in the Schedule of Activities (Section 2), venous blood samples will be collected for measurement of plasma A $\beta$  concentrations.

A maximum of 5 additional plasma samples per subject may be drawn during the study at the discretion of the investigator or sponsor. These additional samples may be drawn to measure LY3323795 or A $\beta$  concentrations.

Plasma concentrations of A $\beta$ 1-40 and A $\beta$ 1-42 and CSF concentrations of A $\beta$ 1-40, A $\beta$ 1-42, CCI will be determined using validated immunoassay methods.

CCI

Plasma and CSF samples collected for PD measurements will have aliquots stored for future exploratory work. The sample(s) will be identified by the subject number (coded) and stored for up to a maximum of 15 years after the last subject visit for the study at a facility selected by the sponsor. Any sample remaining after this period will be destroyed. Research will be limited to investigation of the safety and disposition of LY3323795, PD biomarkers relevant to neurological disease, the mechanism of action of LY3323795, and/or identification of metabolites of LY3323795.

## 9.7. Genetics

A blood sample will be collected for pharmacogenetic analysis as specified in the Schedule of Activities (Section 2), where local regulations allow.

Samples will not be used to conduct unspecified disease or population genetic research either now or in the future. Samples will be used to investigate variable response to LY3323795. Assessment of variable response may include evaluation of AEs or differences in efficacy.

All samples will be coded with the subject number. These samples and any data generated can be linked back to the subject only by the investigative site personnel.

Samples will be retained for a maximum of 15 years after the last subject visit, or for a shorter period if local regulations and/or ERBs/institutional review boards [IRBs] impose shorter time limits, for the study at a facility selected by Lilly or its designee. This retention period enables use of new technologies, response to regulatory questions, and investigation of variable response that may not be observed until later in the development of LY3323795 or after LY3323795 is commercially available.

Molecular technologies are expected to improve during the 15-year storage period and therefore cannot be specifically named. However, existing approaches include whole genome or exome sequencing, genome-wide association studies, multiplex assays, and candidate gene studies. Regardless of technology utilized, data generated will be used only for the specific research scope described in this section.

## 9.8. Biomarkers

Biomarker research is performed to address questions of relevance to drug disposition, target engagement, PD, mechanism of action, variability of patient response (including safety), and clinical outcome. Sample collection is incorporated into clinical studies to enable examination of these questions through measurement of biomolecules including DNA, RNA, proteins, lipids, and other cellular elements.

Plasma and CSF samples for nonpharmacogenetic biomarker research will be collected at the times specified in the Schedule of Activities (Section 2) where local regulations allow.

Samples will be used for research on the drug target, variable response to LY3323795, pathways associated with AD and/or other neurological diseases, mechanism of action of LY3323795, and/or research method, or for validating diagnostic and research analytes, tools, or assay(s) related to AD and/or other neurological diseases.

All samples will be coded with the subject number. These samples and any data generated can be linked back to the subject only by the investigative site personnel.

Samples will be retained for a maximum of 15 years after the last subject visit, or for a shorter period if local regulations and/or ERBs/IRBs impose shorter time limits, at a facility selected by Lilly or its designee. This retention period enables use of new technologies, response to

regulatory questions, and investigation of variable response that may not be observed until later in the development of LY3323795 or after LY3323795 is commercially available.

### **9.9. Health Economics**

This section is not applicable for this study.

## 10. Statistical Considerations and Data Analysis

### 10.1. Sample Size Determination

The sample size of 9 in each cohort of Part A is customary for Phase 1 studies evaluating safety, PK, and/or PD parameters, and is not based on statistical mean estimation.

For Part B, given the CSF A $\beta$  variability observed in prior studies that measured CSF A $\beta$ , the sample size of 5 subjects per LY3323795 dose and 2 subjects per placebo in a parallel cohort, pooled placebo design is sufficient to detect a mean A $\beta$  reduction of approximately 21% or more from baseline. Assuming a standard deviation of 22% for the CSF A $\beta_{1-40}$ , a sample size of 5 subjects per dose would provide approximately 90% coverage probability that the half-width of the 80% CI for the mean of percentage change from baseline of CSF A $\beta_{1-40}$  would be within 21%. For example, if the estimate of the percentage change from baseline CSF A $\beta_{1-40}$  at nadir concentration ( $C_{\text{nadir}}$ ) is 50%, then the confidence limit for the percentage change from baseline would be (29%, 71%).

For Part C, assuming a within-subject variability of 25% for the PK parameter (AUC or  $C_{\text{max}}$ ) of LY3323795, a sample size of 8 subjects would provide approximately 90% coverage probability that the half-width of the 90% CI for the geometric mean ratio of LY3323795 with itraconazole, compared with LY3323795 alone, would be within 0.3 in log scale, or 1.35 in natural scale. For example, if the estimate of the ratio of LY3323795 with itraconazole over LY3323795 alone is 1.2, then the confidence limit would be (88%, 162%).

Subjects who drop out may be replaced at the discretion of the sponsor and investigator to achieve protocol-required completers. In Part A, a replacement subject's treatment assignment will follow that of the subject being replaced but may not require completion of all study periods. In Part B, a replacement subject's treatment assignment will follow that of the subject being replaced. In Part C, all subjects, and any replacements, will be on the same treatment assignment.

Subjects who are randomized but not administered treatment may be replaced to ensure that a sufficient number of subjects complete the study, in accordance with the enrollment numbers given in Section 5.2.

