**Statistical Analysis:**

The sample size for Part A is customary for Phase 1 studies evaluating safety, PK, and/or PD parameters, and is not based on statistical mean estimation. Parts B and C are not formally powered to detect a prespecified anticipated effect; however, precision intervals have been calculated to show what may be observed for changes in cerebrospinal fluid (CSF) A $\beta$  and effect of itraconazole on LY3323795 given the sample sizes.

No formal interim analyses are planned for this study. Interim access to data (IAD) is scheduled to occur throughout the study. The purpose of these IAD reviews is to examine the safety and or PK/PD data and guide dose selections.

All investigational product and protocol procedure adverse events will be listed, and if the frequency of events allows, safety data will be summarized using descriptive methodology. Safety laboratory parameters, vital signs, and electrocardiogram parameters will be listed and summarized using standard descriptive statistics for values at each time point as well as changes from baseline.

PK parameter estimates for LY3323795 will be calculated using standard noncompartmental methods of analysis. The primary parameters for analysis will be Cmax and AUC of LY3323795. Other noncompartmental parameters, such as half-life, apparent clearance, and apparent volume of distribution may be reported.

For Parts A and B, plasma concentrations of A $\beta$ 1-40 and A $\beta$ 1-42 will be summarized for each dose group based on the nadir concentration (Cnadir) and the time to reach Cnadir (tnadir).

In Part B, CSF concentrations of A $\beta$ 1-40, A $\beta$ 1-42, and CCI will be summarized for each dose group based on the Cnadir, tnadir, and the 24-hour average values, expressed as a percentage change from baseline. Statistical analysis of CSF A $\beta$ 1-40 and A $\beta$ 1-42 concentrations obtained over the fixed-scheduled sampling period will be analyzed using a repeated-measures analysis with the primary statistical estimation of the overall mean percentage change from baseline and 90% confidence interval among the LY3323795 doses and placebo at each post dose time point.

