In healthy subjects, CSF indwelling catheter studies conducted by Lilly have shown increases in CSF A $\beta$  concentration over 24 to 40 hours of sampling (Lucey et al. 2015). In these CSF catheter studies, the initial 4-hour sampling interval following the catheter placement showed a 10% to 15% increase in A $\beta$  concentration. Subjects receiving placebo following the catheter placement showed additional increases of 20% to 30% over a 36-hour CSF sampling period. Similar findings were shown by Bateman (2008). Therefore, placebo will also be included in Part B of this study. Previous studies have also shown that CSF A $\beta$  concentrations slowly return to baseline following a treatment that disrupts A $\beta$  synthesis; however, due to the large variability in CSF A $\beta$  concentrations both within and between individuals, a long duration of sampling is required to fully characterize the PD time course.

An assessment of LY3323795 PK with concomitant itraconazole administration is planned in Part C. In vitro recombinant CYP isoform phenotyping studies indicate CYP3A4 is the only tested CYP isoform that metabolizes LY3323795. In vitro metabolism studies with human hepatocytes suggest that CYP-mediated metabolism accounts for approximately 70% of the overall metabolism in hepatocytes. Taken together, these data result in a predicted LY3323795 AUC increase of approximately 4-fold when LY3323795 is coadministered with the strong CYP3A inhibitor itraconazole. Accordingly, coadministration with itraconazole will help determine the clinical relevance of CYP3A inhibition on LY3323795 clearance. The dosing regimen for itraconazole was optimized using a physiologically based PK model with the goal of reaching steady-state concentrations as rapidly as possible (Ke et al. 2014). The use of the oral solution formulation of itraconazole is specified as it has higher bioavailability and less variability in absorption than solid dosage formulations.

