#### 10.3.3.2. Pharmacodynamic Statistical Inference

For Part B of this protocol, statistical analysis of CSF  $A\beta_{1-40}$  and  $A\beta_{1-42}$  concentrations obtained over the fixed-scheduled sampling period will be analyzed using a repeated-measures analysis with the primary statistical inference of pairwise comparison of the overall mean difference among the LY3323795 doses and placebo using a 90% CI. The statistical model may include the baseline CSF  $A\beta_{1-40}$  and  $A\beta_{1-42}$  concentrations obtained during predose CSF collection period and fixed effects of dose groups (placebo and doses of LY3323795), scheduled CSF sampling time, and the interaction between dose groups and sampling times. A compound symmetric covariance structure may be used. From the statistical model, the primary statistical estimates will be the mean percentage reduction from baseline in CSF  $A\beta_{1-40}$  and  $A\beta_{1-42}$  concentrations at each time point with LY3323795 over the 36-hour sampling interval. The above model will fit both the log-transformed and percentage change from baseline in CSF  $A\beta_{1-40}$  and  $A\beta_{1-42}$  concentrations.

CCI

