6.1. General Considerations

Statistical analysis of this study will be the responsibility of Eli Lilly and Company or designee.

It is planned that all safety reporting including eye safety assessments will be conducted by Covance; with the exception of inferential analyses on safety, PK, PD, and biomarkers, which will be conducted by Eli Lilly and Company.

Pharmacokinetic and pharmacodynamic analyses will be conducted on the full analysis set. This set includes all data from all subjects receiving at least 1 dose of the investigational product. Safety analyses will be conducted for all enrolled subjects, whether or not they completed all protocol requirements.

Additional exploratory analyses of the data will be conducted as deemed appropriate. As this is a Phase 1 study and there will be no formal statistical hypothesis testing, any changes to the planned analysis will not necessitate a protocol amendment and will be detailed in the study report.

Unless otherwise stated, all tests of treatment effects will be conducted at a 2-sided alpha level of 0.10 (0.05 each side).

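### Part B's claim to detect a 21% CSF Aβ reduction is a one-group precision figure at the 80% level, not a detectable effect under the planned 90% intervals

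*Protocol*

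**What the plan says.** Protocol 10.1 (Sample Size Determination), repeated in SAP 5.1, states that 5 subjects per LY3323795 dose and 2 placebo subjects per cohort, with placebo pooled, are enough to detect a mean CSF Aβ "reduction of approximately 21% or more from baseline". It attaches no alpha and no power. The next sentence assumes an SD of 22% and gives "approximately 90% coverage probability that the half-width of the 80% CI for the mean of percentage change from baseline" of CSF Aβ1-40 being within 21%. The worked example is an estimate of 50% at nadir with limits (29%, 71%).

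Other sections describe Part B differently:

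- The Protocol synopsis (Statistical Analysis) says "Parts B and C are not formally powered to detect a prespecified anticipated effect" and presents the calculations as precision intervals.
- The synopsis plans estimation of the "overall mean percentage change from baseline and 90% confidence interval among the LY3323795 doses and placebo at each post dose time point".
- Protocol 10.3.3.2, with the same wording in SAP 6.10.2, plans a repeated-measures model with the "primary statistical inference of pairwise comparison of the overall mean difference among the LY3323795 doses and placebo using a 90% CI". It also says that "the primary statistical estimates will be the mean percentage reduction from baseline" at each time point.
- SAP 6.1 says "all tests of treatment effects will be conducted at a 2-sided alpha level of 0.10" unless otherwise stated.
- Protocol 5.4 explains why placebo is needed in Part B: earlier placebo subjects showed "additional increases of 20% to 30% over a 36-hour CSF sampling period".

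**The concern.** A confidence interval half-width says how wide the interval is likely to be. A detectable effect is the true effect at which the interval excludes zero with a stated, high probability. When the true effect equals the half-width, that probability is well below 80 or 90%. The 21% is presented as the second but calculated as the first.

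There are two further mismatches. The sentence credits the pooled placebo design, yet placebo does not enter the calculation. And the interval is at 80%, whereas every interval in the visible Part B analysis text is at 90%. The Part C paragraph of the same section does use the 90% level of its planned analysis.

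Protocol 3.1 treats CSF Aβ reduction as the study's key biomarker and intends it to help choose later doses. Someone reading the Part B results could therefore take 21% as the smallest reduction this design reliably picks up, and misread an interval that includes zero.

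**Working it through.** **Inputs.** n=5 per dose, SD 22%, 80% interval and 90% assurance (Protocol 10.1). Placebo is 2 per cohort over 3 cohorts, so 6 pooled and 21 subjects in 4 groups (Protocol 5.2). Planned level is 90%, two-sided alpha 0.10 (synopsis, Protocol 10.3.3.2, SAP 6.1 and 6.10.2). Assumption: SD 22 percentage points in every group and for the quantity analysed.

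**Formulas.** With ν degrees of freedom:

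- Half-width when the sample SD equals the true SD: t × SE.
- 90%-assurance half-width: t × SE × √(χ²(0.90, ν)/ν).
- Power: noncentral t with noncentrality Δ/SE.
- SE for one group: 22/√5 = 9.84.
- SE for LY minus pooled placebo: 22 × √(1/5 + 1/6) = 13.32.

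**The plan's own figure.** t(0.90, 4) = 1.533, so t × SE = 15.1. χ²(0.90, 4) = 7.78, and 15.1 × √(7.78/4) = 21.04. The probability that the half-width is within 21 is 0.899. This reproduces the stated 21% and the stated 90%. Even at this 80% level, power at a true change of 21 is 73%.

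**At the planned 90% level, SD 22.**

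| Quantity | ν | t | Half-width at SD 22 | 90%-assurance half-width | P(within 21) | Power at 21 |
|---|---|---|---|---|---|---|
| One dose group, own SD | 4 | 2.132 | 20.97 | 29.3 | 0.60 | 55% |
| One dose group, SD pooled over 4 groups | 17 | 1.740 | 17.1 | 20.7 | 0.92 | 66% |
| LY minus placebo, 5 vs 6, SD from 4 groups | 17 | 1.740 | 23.2 | 28.0 | 0.33 | 45% |
| LY minus placebo, 5 vs 6, SD from 2 groups | 9 | 1.833 | 24.4 | 31.2 | 0.33 | 43% |

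The effect with 80% power is 29.9 points for one group with its own SD. For the placebo contrast it is 34.5 points (17 df) or 35.9 points (9 df).

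**Placebo drift.** The 45% is not the power for a 21% fall from baseline. If placebo rises 20 to 30 points, that fall is a contrast of 21+20 = 41 to 21+30 = 51 points, with 90 to 98% power (17 df). If the drift in the analysed quantity is smaller, say an assumed 10 to 15 points, the contrast is 31 to 36 points and power is 72 to 83%.

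**Range of SD** (90% interval; 90%-assurance half-width, power at 21).

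| SD | One group, own SD (4 df) | LY minus placebo (17 df) |
|---|---|---|
| 15 | 19.9, 82% | 19.1, 72% |
| 18 | 23.9, 69% | 22.9, 58% |
| 22 | 29.3, 55% | 28.0, 45% |
| 25 | 33.2, 47% | 31.8, 38% |

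**The case against.** The precision arithmetic is correct, the basis for the 21% is given in the very next sentence, and the synopsis disclaims formal power. That is true, but it does not rescue the claim to detect: the disclaimer contradicts it.

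The strongest technical point is pooling. A repeated-measures model with a common variance would put the analysis nearer 17 df. The 90%-assurance half-width for one group is then 20.7, so both the 21% precision and the (29%, 71%) example survive at the planned 90% level. This stands for precision, and the replacement text should say so. It does not stand for detection, where power is 66%.

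The 21% could also come from a normal-theory formula with known SD, which gives 20.9% at 80% power with one-sided alpha 0.10. That route has no placebo term, does not use the planned level and ignores the t correction at n=5. The documents state none of its settings.

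Placebo drift can make a 21% fall from baseline easy to see against placebo. That is power for a larger contrast, and it is not how the 21% was derived.

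Finally, the SD may not apply. The example is at nadir, whereas the planned inference includes an overall mean over 19 postdose samples. If 22% is a single-time SD under compound symmetry, averaging gives 22 × √((1+18ρ)/19). At an assumed ρ of 0.3, 0.5 or 0.9, power for a 21-point contrast is 83%, 67% or 48%. The documents give no correlation, so this uncertainty stands. It is a reason to state what the 22% refers to.

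**Conclusion.** The statement is wrong as written. The 21% is a correctly computed precision figure for one dose group at the 80% level, and it is presented as a detectable reduction in a placebo-controlled design analysed at 90%. On the plan's SD of 22, taken to apply to every group and to the analysed quantity, power for a 21-point effect is between 43% and 66% on each reading of the planned interval. A smaller effective SD would raise these figures, and the plan gives nothing to settle it. Some of the analysis text is redacted, so the absence of an 80% interval there is a statement about the visible text.

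The point is minor. CSF pharmacodynamics is a secondary objective, and no dose decision depends on an interval excluding zero. For the reductions above 50% that Protocol 5.1.2.1 aims for, power at 50 points is high: 99% for one group (4 df) and 97% for the contrast (17 df).

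**What to change.** In Protocol 10.1 and SAP 5.1, delete the claim that the design suffices to detect a 21% reduction, and replace the 80% interval statement with text such as:

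> Part B is not formally powered. Assuming an SD of 22 percentage points in every group, with 90% probability the half-width of the 90% CI will be within about 29 points for one dose group's mean change from baseline (n=5, own SD, 4 df; about 21 points if the SD is pooled over the four groups, 17 df), and within about 28 points for LY3323795 minus pooled placebo (5 vs 6, 17 df).

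Replace the example and label each quantity:

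- Change from baseline of 50%: about (21%, 79%) with the group's own SD, or (29%, 71%) with the pooled SD.
- LY3323795 minus placebo difference of 50 points: about (22, 78).

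State whether the SD of 22% refers to the nadir value or to a modelled mean.

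The cost is wording in two sections. No subjects are added, and conduct and dose selection are untouched. The stated precision becomes less favourable, except for the one-group mean with a pooled SD, where it stays at about 21 points.
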